### **8.1.2 Definition of Serious Adverse Events (SAE)**

#### **Serious Adverse Event**

Adverse events are classified as serious or non-serious. A **serious adverse event** is any AE that is:

- fatal
- life-threatening
- requires or prolongs hospital stay
- results in persistent or significant disability or incapacity
- a congenital anomaly or birth defect
- an important medical event

Important medical events are those that may not be immediately life threatening, but are clearly of major clinical significance. They may jeopardize the subject, and may require intervention to prevent one of the other serious outcomes noted above. For example, drug overdose or abuse, a seizure that did not result in in-patient hospitalization, or intensive treatment of bronchospasm in an emergency department would typically be considered serious.

All adverse events that do not meet any of the criteria for serious should be regarded as **non-serious adverse events**.

CONFIDENTIAL

This material is the property of the NYU Langone Health. Do not disclose or use except as authorized in writing by the study sponsor

### 8.1.3 Definition of Unanticipated Problems (UP)

#### Unanticipated Problems Involving Risk to Subjects or Others

Any incident, experience, or outcome that meets all of the following criteria:

- Unexpected in nature, severity, or frequency (i.e. not described in study-related documents such as the IRB-approved protocol or consent form, the investigators brochure, etc)
- Related or possibly related to participation in the research (i.e. possibly related means there is a reasonable possibility that the incident experience, or outcome may have been caused by the procedures involved in the research)
- Suggests that the research places subjects or others at greater risk of harm (including physical, psychological, economic, or social harm).

## 8.2 Classification of an Adverse Event

### 8.2.1 Severity of Event

The following guidelines will be used to describe severity of adverse events.

- **Mild** – Events require minimal or no treatment and do not interfere with the participant's daily activities.
- **Moderate** – Events result in a low level of inconvenience or concern with the therapeutic measures. Moderate events may cause some interference with functioning.
- **Severe** – Events interrupt a participant's usual daily activity and may require systemic drug therapy or other treatment. Severe events are usually potentially life-threatening or incapacitating.

### 8.2.2 Relationship to Study Intervention

*The medical monitor's assessment of an AE's relationship to study intervention is part of the documentation process, but it is not a factor in determining what is or is not reported in the study. If there is any doubt as to whether a clinical observation is an AE, the event should be reported. All AEs must have their relationship to study intervention assessed. In a clinical trial, the study intervention must always be suspect. To help assess, the following guidelines are used. [name] will adjudicate the relatedness of AEs to the study participation.*

- **Related** – *The AE is known to occur with the study intervention, there is a reasonable possibility that the study intervention caused the AE, or there is a temporal relationship between the study intervention and event. Reasonable possibility means that there is evidence to suggest a causal relationship between the study intervention and the AE.*
- **Not Related** – *There is not a reasonable possibility that the administration of the study intervention caused the event, there is no temporal relationship between the study intervention and event onset, or an alternate etiology has been established.*

### 8.2.3 Expectedness

[name] will be responsible for determining whether an AE is expected or unexpected. An AE will be considered unexpected if the nature, severity, or frequency of the event is not consistent with the risk information previously described for the study intervention.

## 8.3 Time Period and Frequency for Event Assessment and Follow-Up

We will follow the reporting requirements outlined in the [NYU SOM IRB policies and procedures](#). Figure 4 and Figure 5 are screenshots of the reporting requirements.

CONFIDENTIAL

This material is the property of the NYU Langone Health. Do not disclose or use except as authorized in writing by the study sponsor

#### Figure 4. Definitions of Adverse Event, Unrelated and Related to the Research and Reporting Requirements

[NYU Langone Health IRB | Human Subjects Research Protection Program Policies and Procedures | email [contact]](#)  
indicates that the research procedures caused harm to subjects or others or indicates that subjects or others are at increased risk of harm (including physical, psychological, economic, or social harm) than was previously known or recognized.

##### **A d v e r s e E v e n t**

Any physical, psychological or social harm occurring to subjects during the course of participating in research, whether or not it is related to participation in the research. An Adverse Event can be any unfavorable or unintended event that is temporally related to the research. Examples of Adverse Events include: abnormal laboratory findings, nightmares, broken wrist, upper respiratory tract infection, nausea and vomiting, and other symptoms or diseases. Although Adverse Events occur most commonly in the context of biomedical research, Adverse Events can occur in the context of social and behavioral research.

##### **U n a n t i c i p a t e d**

An event is "Unanticipated" when its nature, frequency, specificity and severity are not expected, given the research procedures described in the protocol-related documents and characteristics of the subject population being studied, and are not accurately reflected in the informed consent document, protocol and/or investigator's brochure.

##### **R e l a t e d t o t h e R e s e a r c h**

An event is "Related to the research procedures" if in the opinion of the Principal Investigator, it was more likely than not to be caused by the research procedures or if it is more likely than not that the event affects the rights and welfare of current subjects.

#### ***R e p o r t i n g R e q u i r e m e n t s***

All Unanticipated Problems, meaning those that are **serious, unexpected, and related to the research activity**, must be reported to the NYU Langone Health IRB. Not all Unanticipated Problems involve direct harm to subjects. Events can occur which are unexpected and result in new circumstances that increased the risk of harm to subjects without directly harming them. In addition, the event may have presented unanticipated risks to others (e.g., the sexual partners of the subjects, individuals the subject may come in contact with, family members, research personnel, etc.) in addition to the subjects. In each case, even if the event did not cause any detectable harm or adverse effect to subjects or others, they nevertheless represent Unanticipated Problems and should be promptly reported under this Policy.

Principal Investigators must report to the IRB as soon as possible, but in all cases within ten (10) working days of becoming aware of and/or receipt of information about any of the following:

- Adverse Events which, in the opinion of the Principal Investigator, are both unexpected and Related to the research. The IRB only requires Unanticipated Adverse Events and Serious Adverse Events that are Related to the research to be reported to the IRB.
- Unanticipated Problem Related to the research that exposes individuals other than the research subjects (e.g., investigators, research assistants, students, the public, etc.) to potential risk.
- Information that indicates a change to the risks or potential benefits of the research. For example:
  - an interim analysis or safety monitoring report indicates that frequency or magnitude of harms or benefits may be different than those initially presented to the IRB, or
  - a paper is published from another study that shows that the risks or potential benefits of the Principal Investigator's research may be different than initially presented to the IRB.
- A breach of confidentiality, including the loss of digital storage devices that contained research data.
- Change in subject's status during the course of their participation in a study that might affect their

CONFIDENTIAL

This material is the property of the NYU Langone Health. Do not disclose or use except as authorized in writing by the study sponsor

Figure 5. Reporting Requirements (con.)

[NYU Langone Health IRB | Human Subjects Research Protection Program Policies and Procedures | email [contact]](#)

eligibility to remain in the study. Examples: Incarceration of a subject in a protocol not approved to enroll prisoners; pregnancy during research participation; children who reach the age of majority (in New York State, age 18) during study participation.

- Change to the protocol taken without prior IRB review to eliminate an apparent immediate hazard to a research subject. For clarity, the NYU Langone Health IRBs do not require reporting of unintentional or intentional changes to the IRB-approved protocol (protocol deviations) unless the deviation was made due to concerns of subject safety or rises to the level of a protocol deviation.
- Complaint of a subject or subject's family member when the complaint indicates unexpected risks or the complaint cannot be resolved by the research team.
- Protocol violation. A protocol violation refers to an accidental or unintentional change to the IRB-approved protocol that harmed subjects or others or that indicates subjects or others may be at increased risk of harm. Examples: receipt of wrong dose of study medication.
- Event that requires prompt reporting to the study sponsor.
- Sponsor-imposed suspension of the research based on risk.

If the Unanticipated Problem is a subject's death, the Principal Investigator should report such event to the IRB no later than five (5) calendar days of becoming aware, whether or not causality (relatedness to the research) has been determined.

The IRB will accept other reports when the Principal Investigator is unsure whether the event should be reported. The Principal Investigator should first contact the IRB Office by email or telephone to determine if the reporting is necessary under this Policy.

Study staff should report the above events electronically using IRB/Research Navigator. The IRB/Research Navigator submission is titled *Reportable New Information*.

If the event requires immediate intervention to prevent serious harm to subjects or others, the investigator may act accordingly to prevent harm and then must report the event within five (5) days.

Investigators must report all other possible Unanticipated Problems occurring at the local research site and non-local research sites to the IRB as soon as possible but no later than ten (10) business days from the date of the event or from the date the investigator is notified of the event.

Problems occurring within thirty (30) days after subjects' active participation or treatment must be reported according to the above schedule.

Investigators or the study team must report possible Unanticipated Problems to the IRB Office in writing using the Unanticipated Problem Reporting Form. The written report should contain the following:

- detailed information about the possible Unanticipated Problems, including relevant dates
- any corrective action, planned or already taken, to ensure that the possible Unanticipated Problems is corrected and will not occur again
- an assessment of whether any subjects or others were placed at risk as a result of the event or suffered any physical, social, or psychological harm and any plan to address these consequences
- any other relevant information
- any other information requested by the IRB Office

A report of a possible Unanticipated Problem involving risks to subjects or others will be immediately forwarded by IRB Office staff to the IRB Chair if the IRB Office staff believes that immediate intervention may be required to protect subjects or others from serious harm.

CONFIDENTIAL

This material is the property of the NYU Langone Health. Do not disclose or use except as authorized in writing by the study sponsor

## **8.4 Reporting Procedures – Notifying the IRB**

There are no anticipated SAE related to this minimal risk study. Any AE or SAE that is determined by the study medical monitor to be related to the study, or an unanticipated problem, will be reported following [the NYU SoM IRB policies and procedures](#) (also see Figure 4 and Figure 5).

### **8.4.1 Adverse Event Reporting**

We recognize that some caregivers might experience psychological distress resulting from learning a new mHealth app during the feasibility trial. Therefore, we will passively monitor any psychological distress reported by caregivers. The term “passive” or “passively” refers to the reliance on voluntary caregiver report, in contrast to the study team’s administration of regular screening throughout the study period to “actively” monitor any changes in psychological distress in caregiver participants.

A summary of all adverse events and serious adverse events will be reported to the NIA Program Officer and the Safety Officer on a quarterly basis.

### **8.4.2 Serious Adverse Event Reporting**

This is a minimal risk study and we do not anticipate any serious adverse events resulting from study participation. Any unanticipated SAE that is determined to be related to this study will follow the following reporting procedure:

#### **Unanticipated Problem Reporting**

Upon notification of any Unanticipated Problems:

1. PI [name] will first notify the NYU Medical Monitor, [name], within 24 hours to determine whether the unanticipated problem is related to study participation.
2. PI [name] will send out a notification email to the IRB, the Emory Roybal Center (to forward the information to the NIA Program Officer), and the Safety Officer within 48 hours of any unanticipated problem that is determined to be related to study participation.
3. PI [name] will also submit a Reportable New Information form in the Research Navigator within 5 calendar days of IRB-reportable AE/SAE/Unanticipated Problems including breaches of confidentiality.
4. Upon advisement by the IRB, NIA, and Safety Officer, PI [name] will determine the study’s status and notify the Study Team.
5. PI [name] will advise the Study Team regarding screening, enrollment, and ongoing participation.

### **8.4.3 Reporting of Pregnancy**

Not applicable.

## **8.5 Reporting Procedures – Notifying the Study Sponsor**

Per [NIA policy](#), all AE that are serious and unexpected should be submitted to the NIA and Safety Officer within 48 hours of the site awareness. The Safety Officer will propose AE and SAE definitions and frequency of monitoring and reporting. A copy of the data safety monitoring plan will be attached to this study protocol once it is approved by the NIA-appointed Safety Officer.

There are no specific stopping rules of the study given that this is a minimal risk study. However, the study may be terminated or suspended based on the judgement of the Safety Officer.

CONFIDENTIAL

This material is the property of the NYU Langone Health. Do not disclose or use except as authorized in writing by the study sponsor

## 8.6 Study Halting Rules

Aim 1 co-design workshop: Not applicable. No intervention will be implemented during the co-design workshop. Participants will only review the proposed intervention contents for the Aim 2 feasibility trial and provide feedback for improvement/refinement. The purpose is to understand the participants' preferences.

Aim 2 Feasibility Trial: This study phase may be temporarily suspended or prematurely terminated if there is sufficient reasonable cause. Safety-related temporary suspension or termination will be determined by the Safety Officer.

Written notification, documenting the reason for study suspension or termination, will be provided by the suspending or terminating party to all investigators, the funding agency, and regulatory authorities. If the study is prematurely terminated or suspended, the PI will promptly inform the IRB and will provide the reason(s) for the termination or suspension.

Circumstances that may warrant termination or suspension include, but are not limited to:

- Determination of unexpected, significant, or unacceptable risk to participants
- Demonstration of efficacy that would warrant stopping
- Insufficient compliance to protocol requirements
- Data that are not sufficiently complete and/or evaluable
- Determination of futility

Study may resume once concerns about safety, protocol compliance, and data quality are addressed and satisfy the sponsor and/or IRB.

## 8.7 Safety Oversight

It is the responsibility of the PI to oversee the safety of the study. Any AE/SAE will first be reported to the PI and then forwarded to the local Medical Monitor, [name], to adjudicate their severity and relatedness to study participation. The Medical Monitor will review all AEs on a regular basis throughout the trial and be available to advise the PI on trial related medical questions or problems. This safety monitoring will include careful assessment and appropriate reporting of AE/SAE following the approved study data and safety-monitoring plan approved by the Safety Officer. Medical monitoring will include a regular assessment of the number and type of serious adverse events. The NIA-appointed Safety Officer will review the data safety monitoring plan and the IRB-approved study protocol. Handeling of protocol deviations is detailed in Section 14.3 below.

Data safety monitoring reports will be submitted to the IRB during the annual [continuing review](#), unlessss a shorter reporting period is required by the IRB.

- **Medical Monitor: [name]**

*[name] is the associate director of the Hartford Institute for Geriatric Nursing and professor in the Departments of Nursing and Medicine at NYU Grossman School of Medicine. He is a board certified geriatric and palliative nurse practitioner who is privileged at NYU Langone to perform research monitoring as a member of the medical and dental staff. As part of his experience and expertise, including in several prior NIH funded extramural awards, [name] will perform assessments of emergent depressive or other psychological symptoms identified in participants and determine the need for referral, treatment, or emergent services.*

Safety oversight will be under the direction of an NIA-approved Safety Officer, [name]. The Safety Officer will evaluate cumulative participant safety data and make recommendations regarding the safety continuation of the study. The Safety Officer will define and approve all data elements needed to assess trial safety.

CONFIDENTIAL

This material is the property of the NYU Langone Health. Do not disclose or use except as authorized in writing by the study sponsor

- **Safety Officer: [name]**

## 9 Study Monitoring

Study site monitoring is conducted to ensure that the rights and well-being of human subjects are protected, that the reported trial data are accurate, complete, and verifiable, and that the conduct of the trial is in compliance with the currently approved protocol/amendment(s), with GCP, and with applicable regulatory requirement(s).

- The PIs will conduct centralized monitoring of all data collected for the feasibility trial; assess data quality on a weekly basis during the weekly PI meetings with 100% data verification; and generate quarterly data monitoring reports.
- The PIs will monitor all visits and study forms to:
  - Ensure maintenance of required study documents
  - Verify adherence to the study protocol
  - Monitor the quality of data collected
  - Ensure accurate reporting and documentation of all adverse events and unanticipated problems
  - Ensure the rights and safety of participants
  - Confirm that the study is conducted in accordance with GCP guidelines
- During weekly PI meetings, the PIs will review all study forms completed in the previous week to ensure:
  - Informed consent has been obtained and documented in accordance with IRB regulations
  - The information recorded on the forms is complete and accurate
  - There are no omissions in the reports of specific data elements
  - Missing visits are indicated on the forms
  - Participant disposition when exiting the study is accurately recorded
  - All errors and corrective actions will be entered into a Data Management Log and the Protocol Deviation Form as appropriate.

## 10 Statistical Considerations

### 10.1 Statistical and Analytical Plans

Statistical considerations of this study are described in the following sections. However, given that this is a small feasibility trial, no additional formal Statistical Analytical Plan will be developed.

### 10.2 Statistical Hypotheses

Primary hypothesis: The Aliviado DSD Caregiving Mastery Program will be feasible, acceptable and usable to family caregivers of persons living with dementia at risk for DSD.

CONFIDENTIAL

This material is the property of the NYU Langone Health. Do not disclose or use except as authorized in writing by the study sponsor

Secondary hypothesis: The Aliviado DSD Caregiving Mastery Program will improve caregivers' delirium knowledge and DSD caregiving mastery, as well as decrease caregiver strain, depression, and burden.

### **10.3 Analysis Datasets**

Aim 1 and Aim 2 samples will be analyzed separately.

### **10.4 Description of Statistical Methods**

#### **10.4.1 General Approach**

Descriptive statistics will be calculated to summarize caregiver characteristics and baseline data. Continuous variables will be presented as mean and standard deviations (or median and interquartile ranges). Categorical variables will be presented as percentages.

#### **10.4.2 Analysis of the Primary Efficacy Endpoint(s)**

The primary endpoint of this study is feasibility, acceptability, and app usability. Descriptive statistics will be calculated to summarize feasibility, acceptability, and app usability outcomes. Estimates will be reported with 95% confidence intervals.

#### **10.4.3 Analysis of the Secondary Endpoint(s)**

Paired t-tests will be performed to compare changes in delirium knowledge and caregiving mastery from baseline to 2 weeks (immediately post training), and changes in delirium knowledge, caregiving mastery, caregiver strain, depression, and burden from baseline to posttest (Week 6); effect sizes (Cohen's d) will be reported for all outcomes. To maintain the familywise error rate, we will use Bonferroni-adjusted alpha to determine significance.

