### **10.5 Sample Size**

Aim 1 co-design workshop: We aim for 5-8 participants per session based on recommendations from Smaradottir et al. and our consultation with a Design Thinking expert from the Emory Roybal Center Design Studio. Accordingly, the target sample size is 8 caregivers (plus 8 on the waitlist).

Aim 2 feasibility trial: Because improvement in delirium knowledge should occur before improvement of caregiver mastery, our power calculation is based on delirium knowledge. Home health aides exposed to the current Aliviado videos demonstrated medium-to-large knowledge gains (Cohen's  $d = .64$ ). We will have 80% power to detect an effect of this magnitude in 26 caregivers, using a Bonferroni adjusted significance level of  $\alpha = .025$ . The expected gains will likely be larger, as previous research with a similar delirium intervention using telephone-based education modules found even greater improvement at 2 weeks (Cohen's  $d = .86$ ) and 2 months ( $d = .87$ ) post-intervention, and our projected sample of 26 will yield >99% power to detect similar effects. To allow for a 12% dropout rate and remain adequately powered, we aim to recruit 30 caregivers.

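### Optional gain in section 10.4.3: Holm's step-down procedure keeps Bonferroni's familywise error control, never rejects less, and rejects more when several effects are real

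*Combined protocol and SAP*

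**What the plan says.** Section 10.4.3 plans two sets of paired t-tests on the secondary endpoints. The first is given as "Paired t-tests will be performed to compare changes in delirium knowledge and caregiving mastery from baseline to 2 weeks". The second covers "changes in delirium knowledge, caregiving mastery, caregiver strain, depression, and burden from baseline to posttest (Week 6"). That makes 2 + 5 = 7 listed comparisons. Cohen's d is to be reported for every outcome. The multiplicity rule is one sentence: "To maintain the familywise error rate, we will use Bonferroni-adjusted alpha to determine significance". No step-down procedure is mentioned, and no adjusted confidence intervals are promised.

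Section 10.5 sizes the trial on one endpoint ("our power calculation is based on delirium knowledge") at d = .64: "We will have 80% power to detect an effect of this magnitude in 26 caregivers, using a Bonferroni adjusted significance level" of .025. The recruitment target follows: "To allow for a 12% dropout rate and remain adequately powered, we aim to recruit 30 caregivers".

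The secondary hypothesis in section 10.2 is that knowledge and mastery rise and that strain, depression and burden fall. Section 10.4.2 treats the primary endpoints descriptively with 95% confidence intervals. Section 10.4.9, on multiplicity, is marked NA. Section 10.1 says that no separate analysis plan will be written.

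**The concern.** The only purpose the plan gives for the Bonferroni adjustment is control of the familywise error rate. Holm's procedure serves that purpose at the same level and with no extra assumption about how the outcomes are related. It can declare more real changes, and the plan asks for nothing that Holm would take away.

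Holm helps when several null hypotheses are false. The plan expects that: all five outcomes are hypothesised to improve, and knowledge and mastery are each tested twice. Section 4.2.2 says these endpoints are meant to support the theory behind the intervention, so the pattern across outcomes matters as well as any single result. Under plain Bonferroni, some real changes may be called non-significant that Holm would have identified at the same error rate. What is at stake is limited to these secondary tests.

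**Working it through.** **Inputs.** From section 10.5: d = .64 (delirium knowledge only), 26 evaluable caregivers, per-test level .025. From section 10.4.3: seven listed tests. Assumed, because the documents do not state them: two-sided tests, a familywise level of .05, correlations of 0 and .5 between change scores, and every effect size other than .64 for knowledge.

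**1. The plan's own figure.** Power of a paired t-test comes from the noncentral t with 25 degrees of freedom and noncentrality .64 × √26 = 3.26. At two-sided .025 it is 80.4%, and 26 is the smallest sample that reaches 80%. One-sided testing would give 88.0%, so the two-sided reading is the one that matches. Recruitment: 26 / (1 − .12) = 29.5, hence 30. Both match section 10.5.

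**2. How the rules differ.** With m tests, Bonferroni compares every p-value with .05/m. Holm orders the p-values, compares the k-th smallest with .05/(m − k + 1), and stops at the first failure. Two facts follow:
- Every Holm threshold is at least .05/m, so Holm rejects whatever Bonferroni rejects.
- The first Holm step is the Bonferroni step, so the chance of at least one rejection is identical.

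**3. Two tests, both d = .64, independent (exact).** Single-test power is .804 at .025 and .880 at .05.
- Per-test power, Bonferroni: .804.
- Per-test power, Holm: .804 + (.880 − .804) × .804 = .865.
- Both rejected: .804² = .646 under Bonferroni; .880² − (.880 − .804)² = .769 under Holm.
- At least one rejected: 1 − (1 − .804)² = .962 under either rule.

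**4. Simulation (26 caregivers, correlation 0 and .5).** For seven tests the Bonferroni level is .05/7 = .00714, and power at d = .64 is 63.2%.

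| Family and assumed effects | Test | Bonferroni | Holm |
|---|---|---|---|
| 2 tests, both .64 | .64 | 80-81% | 85-87% |
| 2 tests, .64 and .20 | .64 | 80% | 80-81% |
| | .20 | 10% | 15-16% |
| 7 tests, all .64 | .64 | 63% | 76-79% |
| 7 tests, four .64 and three .40 | .64 | 63% | 70-72% |
| | .40 | 21% | 31-35% |
| 7 tests, two .64 and five .20 | .64 | 63% | 65% |
| | .20 | 4% | 5-6% |
| 7 tests, four .64 and three null | .64 | 63% | 68% |
| 7 tests, one .64 and six null | .64 | 63-64% | 63-64% |

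The chance of at least one rejection was the same under both rules in every scenario. No simulated trial had a Bonferroni rejection that Holm missed. With four real effects and three nulls, Holm's familywise error was 3.3-3.7%, below .05.

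**The case against.** The strongest reply is that nothing here is wrong. Bonferroni is valid, prespecified and the basis of the sample size, and the promised 80% is delivered. It also gives one fixed threshold per test and simple matching simultaneous intervals, which Holm lacks. The larger gains depend on effects the documents do not supply: .64 is given for knowledge alone, from home health aides; no effect size is given for mastery, strain, depression or burden; and section 10.5 itself expects knowledge to improve before mastery. These are secondary tests in a single-arm pilot, and Cohen's d is reported whether or not a result is significant.

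Most of this stands, and it makes the change optional. It does not remove the advantage. Section 10.5 makes no power statement for the other four outcomes, and section 10.4.3 promises no simultaneous intervals that Holm would forfeit.

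A reader might infer three stronger things that the documents do not support:
- **That the trial throws away planned power.** It does not: the planning level is the Bonferroni level, and 80.4% reproduces.
- **That Holm is more powerful in every case.** It is not: the chance of at least one rejection is identical, and with one real effect among seven the per-test gain is nil.
- **That Holm gains most because the questionnaires are correlated.** The gain comes from several effects being real. With seven tests at .64, Holm's per-test power falls from 79% at correlation 0 to 76% at .5. In mixed scenarios the weaker endpoints do gain somewhat more with correlation.

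**Conclusion.** The point holds as an optional efficiency improvement. For either family the plan could mean (two tests, implied by .05/.025 = 2, or the seven listed), Holm keeps the same familywise guarantee and never rejects less. The per-test gain at 26 caregivers is about 0 to 16 points, and about 5-6 points for two tests both at d = .64. The size depends on how many of the other effects are real. It also rests on the assumed two-sided familywise .05, the assumed correlations, and effect sizes that are mostly not in the documents.

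The choice has no bearing on feasibility, acceptability or usability. The unclear family (two tests implied in section 10.5, seven listed in section 10.4.3, NA in section 10.4.9) is a separate matter. Under Bonferroni it moves power at d = .64 from 80% to 63%, and Holm does not settle it, because Holm also needs a defined family.

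**What to change.** In section 10.4.3, replace the Bonferroni rule with: the Holm step-down procedure at a two-sided familywise level of .05, with Holm-adjusted p-values reported, applied to a family of tests listed by outcome and time point. Section 10.5 may keep .025 as a conservative planning level if that family has two tests.

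The cost is one sentence in an amendment, which section 13.2 requires the IRB to approve. No extra caregivers or data are needed. Holm has no simple matching simultaneous confidence intervals, but none are planned. Because no separate analysis plan will follow, the change belongs in the protocol before outcome data are examined; a switch made after seeing results would not be credible.
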